Transdermal alcohol monitors can provide noninvasive, continuous monitoring of alcohol use by detecting ethanol diffused through the skin.^{27,31} Secure Continuous Remote Alcohol Monitor (SCRAM) anklet (Alcohol Monitoring Systems, Inc.) is the most widely used transdermal monitor but is designed to be used for law enforcement purposes.³² However, wider application of SCRAM anklet in clinical and intervention settings is limited by its shortcomings including its large size, high cost, and social stigma.^{20,25,29} The newest generation of wrist-worn alcohol monitor (BACtrack Skyn) is designed for consumer use and

addresses these limitations. The device looks like a fitness tracker, is inexpensive, samples up to every second, and transmits and shows data in real-time via a smartphone app. These advantages make this wrist-worn alcohol monitor a potentially ideal tool to be incorporated into smartphone-based intervention for alcohol use. However, prior to its application in research, thorough validation investigations of the monitor are needed. In this project, we will validate the Skyn monitor among 20 HIV+ drinkers and 20 HIV- drinkers (as comparison group) in both laboratory and field settings.

Fig.1. BACtrack Skyn Alcohol Monitor

5. Specific Aims:

Aim 1: Assess the validity and reliability of the Skyn monitor through comparison with laboratory grade breathalyzer in two fixed-dose lab alcohol administration sessions (Sec. 4.3, 4.5)

Hypothesis 1a: The monitor will be able to detect alcohol use at a low threshold (e.g., one drink).

Hypothesis 1b: The parameters of transdermal alcohol concentration (TAC) (e.g., peak, time-to-peak, area under the curve) will be correlated with number of drinks and breath alcohol concentration (BrAC).

Hypothesis 1c: The TAC readings in two lab sessions will show high correlation (test-retest reliability).

Aim 2: Validate Skyn monitor in daily life using a 2-week ecological momentary assessment (EMA), and evaluate its acceptability and usability for daily alcohol monitoring (Sec.4.4)

Hypothesis 2a: The monitor detected drinking episodes will correspond with self-reports in EMA.

Hypothesis 2b: The TAC readings will correlate with number of drinks in each drinking episode.

Exploratory Aim: Explore factors (e.g., gender, HIV status) that may be associated with individual differences in monitor readings (e.g., peak, time-to-peak, correlation with consumption level).

6. Research Plan:

Overview

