This study will include two parts: laboratory and field validation of the Skyn monitor (Fig. 2). We will need complete data from 20 HIV+ drinkers (~50% male) and 20 HIV- drinkers (~50% male), but we will screen to 160 participants to account for potential screen failure and drop out. Participants will be invited to complete all components of the study or only the field test portion given the COVID pandemic. The PI will decide who will complete all components and who will complete only the field testing. Participants will first complete an alcohol administration session (Lab Session 1) at the simulated bar lab, where they will consume 3 standard drinks (i.e., 3 12oz beers) at a determined consumption rate (30min). The transdermal alcohol concentration (TAC) readings collected from the Skyn monitor will be compared with breath alcohol concentration (BrAC) and may be compared with the Secure Continuous Remote Alcohol Monitor (SCRAM; Alcohol Monitoring Systems, Inc.) anklet. After completing Lab Session 1, during a two-week field test, participants will use the Skyn monitor and record drinking episodes using an EMA app. After the field test, participants will return to the bar lab to complete a second alcohol administration session using the same procedures as in Lab Session 1 to obtain test-retest reliability of the monitor. They will also complete a questionnaire on the acceptability and usability based on their experience with the Skyn monitor and its smartphone app.

Of note, BACtrack Skyn monitor has been approved in our previous study ([IRB201700455](#) for laboratory alcohol administration study where participants wear the monitor while they self-administer alcohol in the bar lab).

[figure not shown]

Figure 2. Study Procedures

Participants

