practice with the apps and monitor until they feel efficient with all. Further, participants may also be asked to wear the Secure Continuous Remote Alcohol Monitor (SCRAM; Alcohol Monitoring Systems, Inc.) anklet for the duration of the drinking session. The SCRAM anklet is similar to the Skyn device although it is worn around the ankle rather than the wrist. The SCRAM anklet will be used to evaluate whether transdermal alcohol concentration (TAC) readings obtained from each device converge, given that the SCRAM anklet is a validated TAC monitor. The SCRAM anklet has been approved and risk assessed in our previous study ([IRB201700623](#)).

Once practice with apps and monitor is completed, vital signs (including blood pressure, pulse, height and weight) will be collected, urine drug and pregnancy screening will occur, and participants will be provided a light snack (150-200 calories). Next, participants will be asked to complete some questionnaires (e.g., Alcohol Urge Questionnaire (AUQ); Positive and Negative Affect Scale (PANAS); Alcohol Purchase Task (APT); real time impaired control scale (ICRT); and a single-item question asking how much one wants alcohol currently).

Next, the drinking session will begin. We will provide several common beer brands with similar calorie (125-150) and alcohol level (~4.5% ABV) for the participants to choose from. Participants will be instructed to wear the Skyn monitor and SCRAM anklet and drink 3 beers by completing each beer in 15 minutes⁵⁰ with a 15-minute break in between (30min in total for each beer). During this time, the participant's BrAC will be measured every 30 minutes. Following the end of each beer during the 15-minute rest period, participants will also complete a brief packet of questionnaires very similar to the one they completed before drinking, plus the Biphasic Alcohol Effects Scale (BAES) and a single-item question asking how much one likes the effects of alcohol. Alcohol administration will be conducted per NIAAA guidelines⁵¹.

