At the end of the 90-minute drinking period, participants will give breath alcohol readings approximately every 15 minutes for the remainder of the session. Every hour participants will also complete the same brief packet of questionnaires they completed earlier in the session. At the end of the evening participants will remove the SCRAM anklet. All participants are required to remain in the simulated lab or research office for two hours after drinking and until the participant's breath alcohol drops to the safe level of 0.00%. During this time, participants will be provided free Wi-Fi, TV, magazines, snacks and nonalcoholic beverages (e.g., water, juice).

Once the participant's breath alcohol level falls to a BrAC of 0.00%, they will be provided transportation back home. This transportation can only be taken directly home. Transportation will be by car unless the participant resides within a half mile of the research facility, in which case there will be an option for them to walk, along with a member of the study staff. For the participant's safety, it will not be possible for them to drive themselves home or for them to have a friend or family member pick them up.

The whole lab session is expected to last about 5-6 hours, and participants will receive \$15/hour. Payment for drinking session is capped at \$90 as we expect most people will reach .00% by then. Participants who come to their lab session as originally scheduled will be provided an additional \$10 payment.

Field Test. After Lab Session 1 or when “field test only” participants come to the lab to pick up the device, participants will be instructed to wear the Skyn monitor in their daily life for a 2-week period. They can see the readings from the Skyn app on their phone if they want, but not required for this study. They will be allowed to take it off for shower or bath, swimming, charging the device, or when their activities may cause damage to the monitor (e.g., exposure in the rain). Since the monitor also has a temperature sensor, it’s possible to determine whether participants take it off. We will ask participants to check the battery status every other day and charge it if needed. The RA will be available to answer questions over the phone to help troubleshoot remotely, or have the participant bring in the Skyn monitor if they really need in-person assistance with the device itself or the app.

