Analysis plan for Aim 2. *Validate Skyn monitor in daily life using a 2-week ecological momentary assessment (EMA), and evaluate its acceptability and usability for daily use.* H2a. Agreement between monitor and self-reports in EMA. Using the same definition of a successful detection and procedure of determining drinking episode in monitor data as in

H1a, we will calculate the detection rates by self-reported number of drinks. A receiver operating characteristic (ROC) curve will be plotted. H2b: Relationship between TAC and number of drinks. First, simple correlations will be calculated to examine the association between TAC (peak, AUC) and self-reported number of drinks using all drinking episodes. Second, a multilevel analysis will be used to examine the association between TAC (peak, and AUC) and number of drinks accounting for nested data within person. Acceptability and Usability. Ratings of the Skyn monitor will be summarized on aspects such as wearability, ease to operate, satisfaction with the product, and willingness to wear.

Analysis plan for Exploratory Aim. *Explore factors that may be associated with individual differences in monitor readings.* T-tests or Chi-square will be used to examine group differences (e.g., male vs. female, HIV+ vs. HIV-) in TAC parameters (i.e., peak, time-to-peak) and their relationships with # of drinks and BrAC.

Sample size and power. This is for how many participants need to complete the study. For Aim 1, the sample size was based on prior laboratory validation studies of transdermal alcohol monitors.^{36,45,57} Also, power analysis shows that a sample size of 40 will give us 80% power to detect a correlation $\geq .60$. For Aim 2, power analysis shows that $n = 40$ will give us 90% power ($\alpha = .05$) to detect an effect size $\geq .13$ in a multilevel analysis with $r = .60$ between measures.^{58,59} For Exploratory Aim, $n = 20$ in each group can give us 80% power to detect a large difference ($d \geq .80$).

7. Possible Discomforts and Risks:

Potential risks in this study include:

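### Exploratory aim: a regression of peak TAC on group plus peak BrAC, set beside the planned unadjusted comparison, would cheaply help tell a BrAC difference from a TAC difference at equal BrAC

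*Combined protocol and SAP*

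**What the plan says.** The Exploratory Aim (section 5) looks for factors "that may be associated with individual differences in monitor readings". Its analysis plan in section 6 states that "T-tests or Chi-square will be used to examine group differences", and the full scope of the sentence is "group differences (e.g., male vs. female, HIV+ vs. HIV-) in TAC parameters (i.e., peak, time-to-peak) and their relationships with # of drinks and BrAC". No model or covariate is named, and no statistic is given for comparing the relationships.

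The Overview fixes the lab dose for all: participants attend a session "where they will consume 3 standard drinks (i.e., 3 12oz beers"), with no scaling by sex or weight stated. The target is "20 HIV+ drinkers (~50% male) and 20 HIV- drinkers (~50% male"), which is 20 per HIV group and about 10 + 10 = 20 per sex. Some participants may have no lab BrAC, because "The PI will decide who will complete all components and who will complete only the field testing".

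In the lab, during drinking, "BrAC will be measured every 30 minutes"; afterwards "participants will give breath alcohol readings approximately every 15 minutes for the remainder of the session". H1b2 in the Aim 1 plan derives peak BrAC and sets it against peak TAC by correlation with a scatter plot, by Bland-Altman peak differences with a zero-slope check, and by the delay between the BrAC and TAC peaks.

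**The concern.** At a fixed dose, a group can show a higher peak TAC for two reasons: its BrAC was higher, or it gives a higher TAC at the same BrAC. In a study meant to validate a monitor the two have different meanings. The first says little about the monitor. The second suggests that readings may need a group-specific interpretation.

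Read alone, an unadjusted t-test can be significant only because BrAC differs. It can also miss a real difference at equal BrAC when a BrAC gap runs the other way. No main hypothesis depends on this aim and BrAC is collected in any case, so what is at stake is how clearly the exploratory result can be interpreted.

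**Working it through.** **The plan's own figure.** The sample-size paragraph claims 80% power for d = .80 with 20 per group. The t-test (noncentral t, 38 df) gives 79.9% one-sided and 69.3% two-sided at .05. Sidedness is not stated, and alpha = .05 is stated only for Aim 2. Two-sided .05 is used below.

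**Inputs.** From the documents: 20 per group. Assumed: the group gap in peak BrAC, in within-group SDs (0 to 1.0), and the within-group correlation r of peak TAC with peak BrAC (.40 to .80). The plan's .60 is a detectable correlation for Aim 1, not an expected one; it serves here as the central value.

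**Identical TAC response.** With TAC = r × BrAC + noise, the expected standardized TAC difference is r × gap; for example .60 × 0.8 = 0.48. Share of trials significant:

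| BrAC gap (SD) | 0 | 0.2 | 0.5 | 0.8 | 1.0 |
|---|---|---|---|---|---|
| Unadjusted, r = .40 | 5% | 6% | 10% | 17% | 23% |
| Unadjusted, r = .60 | 5% | 7% | 15% | 32% | 46% |
| Unadjusted, r = .80 | 5% | 8% | 23% | 51% | 69% |

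Simulated regression on group plus peak BrAC (37 df) stays at about 5% in these cells, provided that BrAC is error-free and nothing else drives both BrAC and TAC.

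**Masking.** At r = .60 and gap 0.8, let TAC at equal BrAC be lower by .60 × 0.8 = 0.48 SD in the group with the higher BrAC. The unadjusted test finds this in 5% of trials and the adjusted test in about 39%. With 15 or 10 per group the adjusted figure is about 30% or 20%.

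**Precision at zero gap.** Adjustment reduces the residual SD to √(1 − .36) = .80. For a 0.6 SD shift, power rises from about 46% to 63%.

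**Do the H1b2 measures, compared by group, already separate the two explanations?**
- *Correlation.* A level shift leaves it unchanged. With a 0.6 SD shift and r = .60 in both groups, comparing correlations is significant in about 5% of trials.
- *Per-person peak difference.* With k = SD of TAC / SD of BrAC, the slope is b = r × k and the spurious effect is (b − 1) × gap / √(k² + 1 − 2rk). It vanishes only at b = 1. At r = .60, gap 0.8 and identical response, k = 0.5 / 1 / 1.67 / 2 gives 57 / 20 / 5 / 6% significant.
- *Bland-Altman slope.* It equals (k² − 1) / [(k² + 1 + 2rk)/2], which is 0 at k = 1 for any r. A flat plot is therefore compatible with a TAC-on-BrAC slope of .60.
- *Delay between peaks.* For time-to-peak this does the job if compared by group. Rounding error (interval/√12) is about 4.3 minutes at 15-minute and 8.7 minutes at 30-minute sampling.

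**Limits of adjustment (r = .60, gap 0.8, identical response).**
- *Measurement error.* The expected residual is .60 × 0.8 × (1 − reliability). At reliability .80 this is 0.096 SD and the adjusted test is significant in about 6%.
- *Shared cause.* If a part s of r comes from something that raises both BrAC and TAC, the unadjusted bias is (r − s) × gap and the adjusted bias is −s × gap. At s = .20 these are 0.32 and −0.16, and the adjusted test is significant in about 9%. At s = .30 they are 0.24 and −0.24, and it is significant in about 13%, no better than the unadjusted test.

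**The case against.** The strongest reply is that the plan has no defect here. The stated target is monitor readings, and an unadjusted comparison answers that. This stands. A reader might infer that the t-test is invalid or that the plan ignores BrAC; the documents support neither, since the quoted sentence itself commits to comparing relationships with BrAC.

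Much of what is needed is indeed near at hand. The H1b2 delay covers time-to-peak, and the scatter plot, marked by group, could show a level shift by eye. Section 5 also lists correlation with consumption level among the individual readings, and H1b2 is to be run after each beer, so a t-test on a per-person TAC-on-BrAC slope is a possible reading. Such a slope could show a difference in gain but not a constant offset. The gap narrows, but for peak TAC it does not close.

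Three further objections stand and limit the claim. The size rests on assumed gaps and correlations; at a gap of 0.2 SD the unadjusted rate is only 6–8%. BrAC is measured after dosing and lies between group and TAC, so adjustment can leave or even introduce bias. And the device senses ethanol that has passed through skin, so a difference at equal BrAC may come from skin and not from the device. It would be tempting to read the adjusted coefficient as proof of a monitor difference, or to claim that adjustment always restores the 5% level. Neither follows.

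**Conclusion.** The point holds as an optional, inexpensive improvement to an exploratory analysis. The unadjusted tests describe group differences in readings at a fixed dose. They do not by themselves distinguish a BrAC difference from a TAC difference at equal BrAC, and the planned comparison of relationships has no stated method that would reliably do so for peak TAC.

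The size is conditional. For BrAC gaps of 0.5 to 1.0 SD at r = .60, the unadjusted test is significant in 15% to 46% of trials with an identical TAC response, against about 5% adjusted in the ideal case and about 6% to 13% at gap 0.8 under the departures examined. The documents do not show that any such gap exists, so it cannot be said that the planned comparison will mislead. The gain in precision needs no BrAC gap, only a correlation between TAC and BrAC. Adjustment reduces the mixing of the two explanations; it does not always remove it.

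**What to change.** Keep the unadjusted comparison as the answer on readings after a fixed number of drinks. Beside it, for participants with lab sessions:

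- report peak BrAC by group (sex, HIV status);
- fit a linear regression of peak TAC on group plus peak BrAC, with one value per person (such as the mean of the two sessions) or a person random intercept;
- add a group-by-BrAC term, labelled exploratory;
- for time-to-peak, report the BrAC-to-TAC delay by group.

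State in advance that the adjusted coefficient is a group difference in TAC at equal measured BrAC, arising from skin or device, and list BrAC measurement error and shared causes as limits.

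The cost is SAP wording and one or two degrees of freedom; no new data are needed. The model covers lab participants only, so power falls as more people do the field test alone, and the interaction term has low power at 20 per group.

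### The exploratory aim assigns t-tests or chi-square to group differences in how TAC relates to drinks and BrAC, without saying what is tested; an interaction term in a model is the better tool

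*Combined protocol and SAP*

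**What the plan says.** Section 5 (Specific Aims) sets an exploratory aim on "individual differences in monitor readings (e.g., peak, time-to-peak, correlation with consumption level" and names sex and HIV status as example factors. Section 6, Analysis plan for Exploratory Aim, gives the method in one sentence: "T-tests or Chi-square will be used to examine group differences" "in TAC parameters (i.e., peak, time-to-peak) and their relationships with # of drinks and BrAC". The outcomes are therefore of two kinds: TAC parameters, and the relationships of those parameters with drinks and BrAC.

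Two other parts of Section 6 define those relationships:

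- **Analysis plan for Aim 1 (H1b).** Mean peak TAC and area under the curve are calculated at 1, 2 and 3 drinks. TAC and BrAC are related in three ways: a simple correlation of peak TAC with peak BrAC, the paired peak difference (Bland-Altman), and the delay from BrAC peak to TAC peak. All are repeated after each beer.
- **Analysis plan for Aim 2 (H2b).** A multilevel model relates TAC to self-reported drinks, with episodes nested in persons. No group term or interaction is mentioned.

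The power statement for this aim is that 20 "in each group can give us 80% power to detect a large difference", given as d of at least .80.

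**The concern.** A t-test compares means, and chi-square compares proportions. To use either on a relationship, the relationship must first become one number per participant. The plan does not say which number.

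This matters in two places. First, the Aim 1 correlation of peak TAC with peak BrAC is calculated across people, so each group has a single coefficient (one per beer). Neither named test can compare two such coefficients. Second, Section 5 lists correlation with consumption level beside peak and time-to-peak, which points to a per-person correlation. In the field that correlation would rest on however many episodes the participant had in two weeks. A t-test would give a participant with two episodes the same weight as one with ten.

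At stake is a stated question: does the monitor track drinking equally well in HIV+ and HIV- drinkers, and in men and women? If the summary is chosen after the data are seen, the answer may depend on the choice. A per-person correlation could also differ between groups only because one group drinks more often.

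**Working it through.** **1. The plan's power figure.** Inputs from Section 6 (Sample size and power): 20 per group, d = .80. The alpha of .05 is stated only for Aim 2 and is assumed here; sidedness is not stated. Two-sample t-test power by the noncentral t distribution:

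- one-sided .05: 79.9%, which reproduces the stated 80%;
- two-sided .05: 69.3%, with 80% reached at d = .91.

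The figure is for a difference in means. It extends to any per-person summary compared by t-test, with d in SD units of that summary. It does not extend to comparing two correlations or two model slopes.

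**2. Where a t-test works.** A straight-line slope was simulated for each participant over three dose levels, 20 per group, 20,000 runs, with illustrative variances because the documents give none. The t-test on slopes had a type I error of 5.3% and power of 69.5% at d = .80, two-sided. This agrees with the 69.3% above, so a per-person slope is a legitimate t-test outcome.

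**3. Where it does not.** Two groups of 20 were simulated with equal mean peaks but TAC-BrAC correlations of .80 and 0. A t-test on peak TAC rejected in 5.2% of runs, which is alpha. It carries no information on the difference in correlation.

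**4. The per-person field correlation.** Section 6 (Participants) requires at least 5 drinking days in the past 30. At that minimum, and counting one episode per drinking day, the expected number in two weeks is 5/30 x 14 = 2.3.

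Assume a true within-person correlation of .60 and bivariate normal data. Two points always lie on a line, so with two episodes r is +1 or -1. The probability of +1 is 1/2 + arcsin(.60)/pi = .705. The mean is then 2 x .705 - 1 = .41, and the SD is sqrt(1 - .41^2) = .91. Simulation gives the rest:

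| Episodes | Mean r | SD of r | Share negative |
|---|---|---|---|
| 2 | .41 | .91 | 29% |
| 3 | .50 | .60 | 20% |
| 4 | .53 | .46 | 14% |
| 8 | .57 | .27 | 4% |

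All means lie below .60, and the shortfall depends on the episode count. Two groups with the same true correlation but different drinking frequency would therefore differ in expected mean r. Fisher's transformation does not help at two episodes, because r of +1 or -1 transforms to infinity.

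**5. What a direct comparison of group correlations could show.** For 20 vs 20, the standard error of a difference in Fisher z is sqrt(1/17 + 1/17) = .343. At two-sided .05, 80% power needs a difference of (1.960 + .842) x .343 = .961. That corresponds to .80 vs .14, or .90 vs .47. For .80 vs .50 the difference is .549, the ratio to the standard error is 1.60, and power is 36%. For .60 vs .30 it is 20%, and for .80 vs .40 it is 50%. These pairs are assumptions; the documents give none.

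**The case against.** A reader might infer that t-tests cannot address relationships at all, so that this part of the aim has no valid test. The documents do not support that. Aim 1 defines two of its three TAC-BrAC relationships, the paired peak difference and the peak delay, as one value per participant per beer. Either can be compared between groups by t-test. Peaks are taken after each beer, so there are up to three TAC-BrAC pairs per session and six over two sessions. Peak TAC at 1, 2 and 3 drinks gives a per-person slope, and step 2 shows that a t-test on such slopes behaves correctly. For all of these the d of .80 is the right kind of power figure.

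The 2.3 episodes also should not be read as typical. It is the entry minimum, no expected count is given, and Section 7 describes the sample as drinking heavily and often. At eight episodes the per-person correlation is much better behaved.

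Nor do the documents say that the team would declare a difference because a correlation is significant in one group and not in the other. That would be speculation.

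Finally, the aim is exploratory, and none of the hypotheses 1a to 2b depends on it.

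All of this stands, and it limits the point to specification and efficiency. It leaves three gaps: the plan does not name the summary, the between-person correlation is not comparable by the named tests, and the per-person correlation favoured by the aim's wording is the weakest of the available summaries.

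**Conclusion.** The point holds as one of under-specification, with a better method available at almost no cost. The named tests suit means and several per-person summaries. They do not suit the between-person peak correlation, and they serve the field question poorly if the per-person correlation is used.

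The size depends on how often participants drink. Under the assumed true correlation of .60, the per-person value runs from nearly uninformative on two episodes (SD .91) to usable on eight (SD .27), with bias toward zero throughout. At 20 per group, only very large differences between group correlations could be detected, so this part of the aim is estimation whichever method is used. The conclusion that the method needs specifying does not rest on the assumed values; only the magnitudes do.

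Severity is low to moderate. The exploratory label lowers the stakes, but the HIV- group is enrolled as a comparison group and the question is a stated one.

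**What to change.** In the Analysis plan for Exploratory Aim:

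1. Keep t-tests for mean peak, time-to-peak, paired TAC-BrAC peak difference and peak delay.
2. For the field, add group and group x number of drinks to the H2b multilevel model. Participants then contribute according to the information that they provide.
3. For the lab, model peak TAC with group x BrAC, and likewise with group x number of beers. Include a person-level random effect whenever beers or sessions are pooled.
4. Report each group's slope and the slope difference with a 95% confidence interval.
5. In Sample size and power, state that d of at least .80 refers to differences in means, and that slope differences are estimated, not powered.

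A prespecified per-person slope compared by t-test would be an acceptable alternative in the lab.

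The cost is a few sentences, an extra term in a model already planned and a small lab model. No new data are needed. The downside is that the intervals on slope differences will be visibly wide.

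### The Aim 1 power figure does not reproduce (about 99%, not 80%, at r = .60), and the exploratory 80% at d = .80 holds only for a one-sided test that the plan does not declare

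*Combined protocol and SAP*

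**What the plan says.** The sample size paragraph in section 6 (Research Plan, Sample size and power) gives two reasons for the Aim 1 number. First, "the sample size was based on prior laboratory validation studies of transdermal alcohol monitors". Second, "power analysis shows that a sample size of 40 will give us 80% power to detect a correlation" of .60 or more. For the Exploratory Aim it says that 20 "in each group can give us 80% power to detect a large difference", defined as d of .80 or more.

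Alpha of .05 appears once, in the Aim 2 sentence between these two. No sentence says whether any test is one- or two-sided, and no null value is given for the correlation.

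The counts are completers, as the paragraph itself says. The Overview agrees: "We will need complete data from 20 HIV+ drinkers" and the same number of HIV- drinkers, about half of each group male.

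The Aim 1 analysis plan calls for a simple correlation of peak TAC with peak BrAC. Hypothesis 1b predicts only that TAC parameters correlate with number of drinks and with BrAC. For the Exploratory Aim, "T-tests or Chi-square will be used to examine group differences", with sex and HIV status as the examples and no predicted direction.

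**The concern.** A correlation of .60 is strong, and 40 pairs are many for detecting it against zero, so 80% looks too low. For the group comparison, 20 per group at d = .80 looks too few for 80% in a two-sided t-test. The two figures therefore seem to err in opposite directions, and the missing alpha and sidedness prevent a reader from recovering either.

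The stakes differ. Understated power for Aim 1 misdescribes what the study can detect but leaves it adequately sized. Overstated power for the Exploratory Aim matters more. The Abstract presents the project as the first validation of this monitor in HIV+ drinkers with an HIV- comparison, and a null HIV or sex comparison read against a claimed 80% power would look more reassuring than it should.

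**Working it through.** **Inputs from the plan.** Aim 1: n = 40, r = .60, stated power 80%. Exploratory Aim: 20 per group, d = .80, stated power 80%. No dropout adjustment is needed because the counts are completers.

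**Assumptions.** Alpha = .05 for both aims, carried over from the Aim 2 sentence. Null correlation zero, from the wording of Hypothesis 1b.

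**Aim 1, power at n = 40 (Fisher z).** Power = Φ(atanh(r) × √(n − 3) − z), with z = 1.960 two-sided or 1.645 one-sided.

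- atanh(.60) = 0.693 and √37 = 6.083; their product is 4.216.
- Two-sided: Φ(4.216 − 1.960) = Φ(2.256) = 98.8%.
- One-sided: Φ(4.216 − 1.645) = Φ(2.571) = 99.5%.
- Simulating the t-test of r under bivariate normality (200,000 runs) gives 98.9% and 99.5%.

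The stated 80% does not reproduce under either sidedness.

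**Aim 1, what n = 40 detects with 80% power.** r = tanh((z + 0.842) / √37).

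- Two-sided: tanh(2.802 / 6.083) = .43.
- One-sided: tanh(2.486 / 6.083) = .39.

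**Aim 1, what would give 80% at r = .60.**

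- A smaller alpha: two-sided power is still 95.0% at .01, 91.2% at .05/12 and 82.3% at .001. Reaching 80% needs alpha of about .0007.
- A non-zero null: about .23 two-sided or .28 one-sided. The plan states none. The .7 reliability benchmark under H1c cannot serve, because it exceeds .60.
- A smaller n: at n = 20, Φ(0.693 × √17 − 1.960) = Φ(0.898) = 81.5% two-sided.

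**Exploratory Aim (noncentral t).** Degrees of freedom 38; noncentrality = .80 × √(20/2) = 2.530.

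| Test at alpha .05 | Critical t | Power at d = .80 | d for 80% power |
|---|---|---|---|
| Two-sided | 2.024 | 69.3% | .91 |
| One-sided | 1.686 | 79.9% | .80 |

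The stated 80% reproduces one-sided only. Two-sided, 80% power at d = .80 would take 26 per group, or an alpha of about .10 with 20 per group. Two-sided type II error at d = .80 is 100% − 69.3% = 30.7%.

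**The two figures together.** At alpha .05, a one-sided test gives 99.5% and 79.9%, and a two-sided test gives 98.8% and 69.3%. Neither yields 80% for both.

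**The case against.** The strongest reply is that the exploratory figure is not a miscalculation. It is right for a one-sided test at .05, the plan does not exclude one, and the two-sided reading is an inference. That is fair as far as it goes: the sentence is under-specified, and it is wrong only once the test is two-sided. But the comparisons are described simply as differences between groups, with no direction given in the analysis plan or the aim. A one-sided test would need a declared direction.

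A second reply is that alpha and the zero null for Aim 1 are also inferred, and that the line may simply carry the wrong n: 20, one HIV group, gives 81.5%. This is plausible but unconfirmed. The printed sentence says 40 and would still need correcting. No customary alpha and no null stated in the plan rescues it.

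A third reply concerns weight. The Aim 1 error is conservative, since 40 participants do give at least 80% power for correlations of .60 or more, and that sample size also rests on prior validation studies. The other aim is labelled exploratory, and no decision rule treats non-significance as evidence of no difference. All of this stands. It limits the consequence to how the results are described and read.

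**Conclusion.** The concern holds. The Aim 1 sentence is wrong as written: power at r = .60 with 40 participants is about 99%, not 80%, whichever sidedness is used, and the 80%-detectable correlation is about .43 two-sided (.39 one-sided), not .60. The exploratory sentence is right only for an undeclared one-sided test. On the two-sided reading that fits the planned comparisons, power is 69%, about 11 points below the claim, and the 80%-detectable difference is d of about .91.

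These results assume alpha .05 for both aims and, for Aim 1, a zero null. The Aim 1 conclusion is insensitive to any usual choice of alpha; the exploratory conclusion depends on sidedness. The design is not underpowered for Aim 1. What needs correcting is the stated power, chiefly the exploratory figure, which errs in the unfavourable direction.

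**What to change.** First confirm the inputs behind both figures. For Aim 1, check whether 80% was computed for one HIV group of 20 or against a non-zero null; if so, say so. For each aim, state alpha, sidedness and, for the correlation, the null value.

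Unless another basis is confirmed, the text could read: With two-sided alpha .05, 40 participants with complete laboratory data give 80% power for a correlation of about .43 or more against zero (about 99% at .60), and 20 per group give 80% power for a standardised difference of about .91 or more (69% at .80).

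If one-sided group comparisons are intended, declare them, give the direction for each factor, and keep the 80% at d = .80 on that basis.

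The cost is rewording two sentences. Sample size and analyses do not change. The Aim 1 claim becomes more favourable, and the exploratory claim becomes less favourable if the tests are two-sided.
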